**Study Devices:**

**PINPOINT® Endoscopic Fluorescence Imaging System**

An endoscopic fluorescence imaging system for high definition (HD) visible (VIS) light and near infrared (NIR) fluorescence imaging that includes the following components:

- A surgical endoscope optimized for VIS/NIR illumination and imaging.
- A camera head that is also optimized for VIS/NIR imaging and mounts to the endoscope eyepiece
- A flexible light guide cable.
- An endoscopic Video Processor/Illuminator for VIS/NIR illumination to the surgical endoscope via a flexible light guide cable, and the image processing required to generate simultaneous, real-time HD video color and NIR fluorescence images.
- A high-definition medical video recorder that allows the capture of still images and video.
- The PINPOINT PAQ containing the imaging agent and aqueous solvent.

**SPY ELITE® Intraoperative Perfusion Assessment System.**

An open intraoperative fluorescence imaging system for HD and NIR fluorescence imaging that includes the following components:

- SPY Elite® Device
- SPY Elite® PAQ containing the imaging agent, aqueous solvent and sterile drape.

The imaging agent used is indocyanine green (ICG), which is a sterile, water-soluble tricyanocyanine dye with a peak spectral absorption at 800-810 nm in blood plasma or blood. ICG contains not more than

5.0% sodium iodide.

**Study Variables:**

**Primary:**

Incidence of post-operative anastomotic leak in each study arm.

**Secondary:**

- Proportion of PERFUSION arm subjects in whom the PINPOINT or SPY Elite system provided sufficient visualization for assessment of blood flow and related tissue perfusion during the procedure.
- Incidence of post-operative abscess in each study arm.

**Safety:**

- Incidence of treatment related adverse device events and surgical complications.
- Clavien-Dindo grading of post-operative complications.
- Concomitant medications and procedures.

**Study Procedures and Assessments:**

The following tests and procedures will be performed:

- Assessment of eligibility criteria.
  - Demographics, vital signs, height, weight, surgical predictive factors.
  - Hemoglobin measurement (pre-operative and Day 1).
  - Randomization to the PERFUSION or STANDARD Arm.
  - Low anterior resection according to surgeon's standard practice inclusive of the hospital/institution's standard pre-operative, post-operative and post discharge care.
    - Circular stapled or transanally hand sewn anastomosis.
    - Open or minimally invasive low anterior resection
    - Minimally invasive low anterior resection with or without hand-assist.
    - Minimally invasive low anterior resection with or without open-assist.
    - Conversion to open procedure.
    - Colorectal or coloanal reconstruction with or without reservoir/pouch.
    - Proximal diverting ileostomy as indicated.
  - PERFUSION Arm (only):
    - Imaging agent administration via central/peripheral IV line.
    - Perfusion assessments of colon transection margin prior to proximal transection.
    - Perfusion assessment of the proximal and distal mucosal aspect of completed anastomosis (except hand sewn coloanal anastomosis).
  - Assessment of adverse device effects up to 24 hrs. post-surgery.
  - Documentation of actual surgical technique.
  - Assessment of anastomotic leak, adverse events and other post-operative complications.
    - CT scan if clinical suspicion of anastomotic leak.
  - Classification of adverse events and post-operative complications using Clavien-Dindo system (Table 2).
  - Ileostomy closure.
    - Routine endoscopy and/or contrast enema of anastomosis between 3 weeks post-surgery and Week 8 visit if subject has an ileostomy.
  - Concomitant medications.
  - Follow-up visits on Day 1, date of discharge, Week 8, and date of ileostomy closure (if applicable). Subjects with a discharge date later than Week 8, who do not have an ileostomy, will have the last study visit at Week 8 visit. The last study visit for subjects with an ileostomy will occur on the date of closure, or at Week 8, whichever is earlier.
- Surgeon Qualification:**
- Training on use of PINPOINT by qualified Novadaq representatives.
  - Perform at least 3 perfusion assessment (proximal and transanal perfusion assessments) procedures with PINPOINT prior to enrolling subjects in the study.
  - Training on use of SPY Elite by qualified Novadaq representatives.

- Perform at least 3 perfusion assessment procedures (proximal only) with SPY Elite prior to using SPY Elite in the study.

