**TABLE 1. Schedule of Events**

Procedure	Baseline (Day -30 to Day 0)	Day 0 (Operative Phase)			Post-Operative Follow-Up			
		Pre-Op	Intra-Op	Post-Op	Day 1 (24±12 hrs.)	Date of Discharge a	Ileostomy Endoscopy/ Contrast Enema (Week 3 to Week 8 ±14d)	Week 8 (56±14d)
Informed consent	X							
Demography	X							
Vital signs, height, weight	X							
Surgical risk factors	X							
Pre-operative diagnosis	X							
Pregnancy test (record in source only)	X							
Inclusion/exclusion criteria	X							
Serum sodium, bilirubin, creatinine and INR for MELD Score	X							
Hemoglobin, Albumin, Pre-albumin		X	X c		X			
Randomization (in OR, during anesthesia)			X					
LAR surgical procedure			X					
Imaging agent administration (treatment group only)			X					
Perfusion Assessment (Perfusion arm only)								
Proximal transection margin			X					
Mucosal aspect of completed anastomosis			X					
Document actual surgical technique				X				
Anastomotic leak assessment				X	X	X		X
Surgical Complication assessment/grading			X	X	X	X		X
Endoscopy and/or contrast enema - Ileostomy subjects (between 3 & 8 wks.)							X b	
Concomitant medications and procedures	X	X	X	X	X	X		X
Adverse events/adverse device effects		X	X	X	X	X		X d

a Subjects with a discharge date later than Week 8, who did not have an ileostomy, will be followed until Week 8 ±14d.

b All subjects with a diverting ileostomy must have endoscopy and/or contrast enema between 3 weeks post-surgery and the Week 8 visit.

c Hemoglobin measurement at time of anastomosis if subject had any hypotensive events or blood loss over 500 ml at time of anastomosisd. All subjects with adverse events thought to be related to the LAR procedure or the PINPOINT or SPY Elite system will be followed until resolution or deemed chronic.

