## **9 EVALUATION, RECORDING, AND REPORTING OF ADVERSE EVENTS**

All untoward medical occurrences either observed by the Investigator or one of his/her medical collaborators, or reported by the subject spontaneously, or in response to the direct question below, will be reported as follows:

- All events occurring before randomization should be recorded in the source documents and will be considered part of the subject's case history.
- Events occurring as a result of the surgery will be reported as adverse events related to the surgical procedure in the adverse event CRF.
- All adverse events occurring during the study will be recorded as adverse events on the adverse event CRF.
- Events related to the use of PINPOINT or SPY Elite will be recorded as adverse device effects in the description of event section of the adverse event CRF.
- Events related to PINPOINT or SPY Elite that affect a user of the device (non-patient) are recorded on the technical complaint form.

In an attempt to optimize consistency of AE reporting across centers, the subjects must be asked a standard question to elicit events. At each clinic evaluation of the subject, study personnel will ask the following questions: "Have you had any problems since your last visit?"

AEs reported on the CRF will include the date of onset, severity, relationship to PINPOINT or SPY Elite, relationship to surgical procedure, date of resolution (or the fact that it is ongoing or has become chronic), action taken, and whether the AE is serious or not.

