#### 9.1.2 Adverse Device Effect (ADE)

Any adverse event related to the use of PINPOINT or SPY Elite (includes imaging agent and all hardware components).

- Includes any event that is a result of a use error or intentional misuse.

ADEs that affect subjects will be recorded as ADEs in the AE CRF. ADEs that only affect a user (non-patient) are recorded in the technical complaint form only.

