## 9.5 Follow-up for Adverse Events and Adverse Device Effects

Throughout the study to the final study visit contact, ADEs will be followed until they resolve or become chronic. All AEs will be followed throughout the study until the Week 8 visit. All AEs related to the PINPOINT, SPY Elite or the surgical procedures, as determined by the Investigator, will be followed until resolution or deemed chronic.

At the final study visit, new AEs, as well as follow-up information for continuing AEs, will be recorded in the CRF and source document. If an SAE or UADE is unresolved at the final study visit, it will be followed by the Investigator until it resolves or becomes chronic (as judged by the Investigator). Follow-up data for such SAEs will be recorded in the source document and reported to the safety contacts. Non-serious ongoing AEs will be followed beyond the final study visit at the discretion of the Investigator.

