3.2 Visit Schedule and Visit Windows

Baseline/Screening Procedures (Day -30 to Day 0)

After signing the informed consent form, subjects will be assigned a screening and be evaluated for eligibility into the study.

The following procedures will be conducted during the baseline assessment:

	Forms			
	Title	Statistical Analysis Plan Template		
	Code	Version	Effective Date	Page
	FRM_ST03_032	01	23 Apr 2015	8 of 20

- Collection of demographics, surgical risk factors, pre-operative diagnosis.
- Vital signs (heart rate and blood pressure), height and weight.
- Serum tests (bilirubin, sodium, creatinine and INR) for MELD Score.
- Pregnancy test (urine test or institution standard of care) for females of childbearing potential.

Day 0 Procedures

On Day 0, the following will be completed before randomization and surgery:

- Serum hemoglobin, prealbumin, and albumin measurement.

During anesthesia, subjects will be randomized. Subjects are considered enrolled upon randomization.

According to the randomization assignment, subjects in the PERFUSION arm will receive perfusion assessment with PINPOINT and/or SPY Elite during surgery and undergo surgery according to the surgeon's standard practice. Subjects randomized to the Standard arm will undergo the surgery according to the surgeon's standard practice only. All subjects will receive the hospital/institution and surgeon's standard pre-operative and post-operative care with the addition of any study specific requirements.

An intra-operative measurement of hemoglobin should be performed at the time of anastomosis if the subject experiences a hypotensive event requiring intraoperative management (e.g. use of vasopressors) or blood loss greater than 500 ml at the time of anastomosis.

Post-operative Follow-up Visits (Day 1 to Last Study Visit)

Subjects will have standard of care assessments throughout the study according to the hospital/institutions standard procedures as well as study specific visits on postoperative Day 1, the date of discharge, Week 8 (56 ±14 days) and the date of ileostomy closure, if applicable. Subjects will be assessed for the following throughout the study:

- Serum hemoglobin measurement (Day 1).
- Evidence of anastomotic leak.
- Assessment and grading of post-operative complications.
- Concomitant medications and procedures.
- Adverse events/adverse device effects.

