- c Hemoglobin measurement at time of anastomosis if subject had any hypotensive events or blood loss over 500 ml at time of anastomosis
- d All subjects with adverse events thought to be related to the LAR will be followed until resolution or deemed chronic.

	Forms			
	Title	Statistical Analysis Plan Template		
	Code	Version	Effective Date	Page
	FRM_ST03_032	01	23 Apr 2015	12 of 20

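### The protocol synopsis ends assessment of adverse device effects at 24 hours, but both schedule tables and the SAP text run it to Week 8, so sites may classify later device-related events differently

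*Protocol*

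**What the plan says.** **Short window.** The Protocol Summary, under Study Procedures and Assessments, lists "Assessment of adverse device effects up to 24 hrs. post-surgery". A separate item in the same list covers leak, adverse events and other complications and carries no time limit, so the cap applies to device effects alone.

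**Long window.**
- Protocol Table 1 has one combined row, "Adverse events/adverse device effects", marked at pre-op, intra-op, post-op, Day 1, discharge and Week 8.
- SAP section 3.2 introduces its list of assessments with "Subjects will be assessed for the following throughout the study", and adverse events/ADEs are on that list. The SAP's Table 1 marks the same row through Week 8.

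**No window.**
- Protocol section 9.1.2 makes any adverse event related to either device, imaging agent included, an ADE whenever it occurs.
- Protocol section 9, on how the adverse event CRF is completed, says "Events related to the use of PINPOINT or SPY Elite will be recorded as adverse device effects in the description of event section", again without a cut-off.
- The first-listed safety endpoint (Protocol Summary, Study Variables; SAP section 3.6) is the incidence of device events and surgical complications, with no period attached.
- SAP section 7 tabulates ADEs and unanticipated ADEs (UADEs) in the safety set, also with no period.

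**Follow-up of known events.** Protocol section 9.5 says "Throughout the study to the final study visit contact, ADEs will be followed until they resolve or become chronic", and, on new events, "At the final study visit, new AEs, as well as follow-up information for continuing AEs, will be recorded in the CRF and source document". Footnote d to the SAP's Table 1 reads "All subjects with adverse events thought to be related to the LAR will be followed until resolution or deemed chronic"; the protocol's footnote d also names the two imaging systems.

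**The concern.** ADE incidence is the first safety endpoint listed for a device trial. If one site stops asking whether an event is device-related after 24 hours and another asks until Week 8, the reported proportion depends partly on which page each site worked from. For the ADE count the direction is clear: a shorter window can only lower it.

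The classification also has uses beyond one table. UADEs are defined in protocol section 9.1.4 as a subset of ADEs, the sponsor screens ADE reports for UADE status (section 9.7), and the monitoring committee receives an ADE summary (section 13.3).

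The protocol itself allows for device effects that appear late. Section 9.1.2 counts events resulting from use error, and section 7.3 lists infection and thrombosis among the risks of a line placed solely for the imaging agent.

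**Working it through.** There is no planned figure to reproduce. The check sets the current texts side by side.

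| Place | What it governs | Period |
|---|---|---|
| Protocol Summary, procedures list | ADE assessment | to 24 hours |
| Protocol Table 1 | AE and ADE assessment | pre-op to Week 8 |
| SAP 3.2 text | AE and ADE assessment | throughout the study |
| SAP Table 1 | AE and ADE assessment | pre-op to Week 8 |
| Protocol 9 and 9.1.2 | ADE recording and definition | none stated |
| Safety endpoint; SAP 7 | ADE counting | none stated |
| Protocol 9.5 | mainly follow-up of identified ADEs | to final visit, or resolved/chronic |

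**Step 1: do the assessment rows conflict?** Yes. Week 8 is 56 ± 14 days, that is 56 − 14 = day 42 to 56 + 14 = day 70, against 1 day in the synopsis. Even the Day 1 visit conflicts in part: 24 ± 12 hours is 24 − 12 = 12 to 24 + 12 = 36 hours, so a visit within its window can fall after the synopsis limit.

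**Step 2: does another text settle it?** No. The endpoint and SAP section 7 name no period. The SAP does not adopt 24 hours anywhere, but it does not state a counting window either.

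**Step 3: what happens to a device-suspected event on Day 3?** Section 9 requires all adverse events during the study on the CRF, with their relationship to PINPOINT or SPY Elite. The event is therefore recorded, and if marked as related it meets the ADE definition. A site following the synopsis may nonetheless not assess it as an ADE. The failure is one of classification, not capture.

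**Step 4: can the size be derived?** No. The calendar ratio is 1/56 = 1.8% (1/70 = 1.4% to 1/42 = 2.4% over the Week 8 window), but that is a share of time, not of risk. Imaging is intraoperative and protocol section 8.3.2.1 gives a plasma half-life for the agent of about 1 to 3 minutes, so device-related risk cannot be taken as uniform over follow-up.

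**Step 5: does footnote d matter to incidence?** No. It concerns following known events to resolution. Protocol footnote d and section 9.5 still require that for device-related events.

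**The case against.** The strongest reply is that this is one stray phrase in a synopsis, with Table 1, sections 9 and 9.1.2 and the whole SAP on the other side, and that the data are collected anyway. Much of that stands, and it rules out several stronger readings a reader might draw:

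- *Late device effects would be missed altogether.* Not supported. All adverse events are recorded with device relationship, and the safety tables are split by actual device use, so an event not labelled an ADE still appears among the adverse events.
- *UADE reporting stops at 24 hours.* Not supported. The 24 hours in section 9.3 is a reporting deadline from discovery of an SAE or UADE, and section 9.7 screens ADE reports with no post-surgical limit.
- *The endpoint itself has two windows.* Not quite. The endpoint states none; the conflict lies in the assessment schedules.
- *Section 9.5 proves the longer window.* Only in part. Its ADE sentence mainly concerns events already identified. It helps because new adverse events are still recorded at the final visit and an ADE is an adverse event by definition.
- *Only about 2% of device risk is covered.* Not supported, as the ratio measures calendar time.

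What the reply does not remove is that the synopsis gives sites an explicit limit that contradicts the schedule, and that nothing in the SAP says how a later event is to be counted.

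**Conclusion.** The inconsistency is real and is between current texts. Its consequence is limited: inconsistent assessment and classification of device-related events after 24 hours, with possible under-counting of a descriptive safety endpoint. The size is unknown and cannot be bounded from the documents. The primary leak comparison, its significance level and the sample size are not touched.

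This rests on two assumptions: that some sites would follow the synopsis literally, and that the device-relationship field is completed for adverse events at any time, as section 9 requires. If the field is reliably completed, the analysis can recover the correct count. If sites stopped considering the device after 24 hours, it can recover the count only in part.

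**What to change.** 1. **Protocol Summary, procedures list.** Reconcile it with Table 1 and the SAP by removing the 24-hour limit on ADE assessment.
2. **SAP section 7.** State that ADEs and UADEs are counted from Day 0 through the last study visit (Week 8), and that ADE status is taken from the device-relationship field of the adverse event CRF. The synopsis puts the last visit of subjects with an ileostomy at closure or Week 8, whichever is earlier, so the clause should say how those subjects are handled.
3. **Separate minor alignment.** Restore the device wording in footnote d of the SAP's Table 1 to match the protocol's footnote d. This affects follow-up wording only, not incidence.

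The cost is one protocol phrase, one SAP sentence and one footnote; no visit or form is added. Reported ADE incidence may be slightly higher. The SAP takes in subjects enrolled through March 31, 2017 and was finalised on 10 Apr 2017, so the second item does most of the work for subjects already treated.

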Subjects in the PFN Arm may also undergo additional or repeat intraoperative imaging using PINPOINT and/or SPY Elite NIR fluorescence imaging based on the surgeon's clinical judgment.

Subjects in the STD Arm will undergo a LAR according to the surgeon's standard practice only.

All subjects will receive the hospital/institution and surgeon's standard pre-operative, post-operative and post discharge care with the addition of any study specific requirements. An air leak test on all anastomoses (with the exception of hand sewn coloanal anastomosis when applicable) will be performed in the surgeon's standard fashion.

Details of the actual surgical technique will be documented post-operatively. The surgeon's ability to sufficiently assess blood flow and related tissue perfusion using PINPOINT or SPY Elite will be recorded. The final height of the anastomosis from the anal verge will be determined by assessing the markings on the stapler or by rigid proctoscopy, at the discretion of the surgeon. The site of the proximal anastomosis segment and the level of the inferior mesenteric artery and vein ligation will also be recorded.

*Follow-up and Post-operative Complications:*

All subjects will be followed to monitor occurrence of post-operative complications up to Week 8 post-surgery ( $\pm 14d$ ). All subjects will have study specific follow-up visits on Day 1, date of discharge, Week 8 and the date of ileostomy closure (if applicable). Subjects with a discharge date later than Week 8 who did not have an ileostomy, will be followed until the Week 8 visit. All subjects with a diverting ileostomy must have flexible sigmoidoscopy or proctoscopy and/or contrast enema to evaluate the anastomosis between 3 weeks postoperatively and the Week 8 visit ( $\pm 14d$ ).

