All subjects will be followed to monitor occurrence of adverse events (AE) and post-operative complications up to Week 8 (56 ±14 days) post-surgery. All subjects will have study specific follow-up visits on Day 1, date of discharge, Week 8 and the date of ileostomy closure (if applicable). Subjects with a discharge date later than Week 8, will be followed until discharge if the Investigator documents that the extended hospitalization is directly related to the surgical procedure or the PINPOINT and/or SPY Elite System. All subjects with a diverting ileostomy must have endoscopy and/or contrast enema of the anastomosis between 3 weeks post-surgery and the Week 8 visit (±14 days).

Subjects who present with a clinical suspicion of anastomotic leak during the study who do not clinically require an urgent reoperation will have a CT scan with PO and, if necessary, rectal contrast to confirm. A leak is considered confirmed if endoluminal contents (air, fluid, GI contents or contrast material) through the anastomosis is identified by imaging, drain output or at reoperation. The scans will be reviewed by an independent radiologist for confirmation. The presence of infection or abscess thought to be related to the anastomosis may be classified as an anastomotic leak at the surgeon's discretion even if it cannot be definitively identified as visualized during an operation or by contrast extravasation. All anastomotic leaks will be followed until resolution.

For patients with a diverting ileostomy, a leak may be identified by direct visualization of an anastomotic defect via sigmoidoscopy or by rectal contrast imaging, regardless of presence or absence of clinical symptoms.

All AE and post-operative complications occurring during the study period will be reported and graded according to the Clavien-Dindo system^20.

Analysis of anastomotic leak rate will be based on the occurrence of a leak according to the protocol definition at any time during the study up to Week 8.

This study is evaluating the utility of the PINPOINT or SPY Elite system only, and therefore the study protocol describes the requirements and use of these devices only.

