#### **8.4 Post-operative Follow-up Visits (Day 1 to Last Study Visit)**

Subjects will have standard of care assessments throughout the study according to the hospital/institutions standard procedures as well as study specific visits on postoperative Day 1, the date of discharge, Week 8 (56 ±14 days) and the date of ileostomy closure, if applicable. Subjects will be assessed for the following throughout the study:

- Serum hemoglobin measurement (Day 1).
- Evidence of anastomotic leak.
- Assessment and grading of post-operative complications.
- Concomitant medications and procedures as described in Section 7.2.
- Adverse events according to Section 9.

Although the patient may be seen by various individuals post-surgery, the study-specific visits must be conducted by a surgeon who is part of the study and has signed the Signature and Delegation Log. Any complications and outcomes of study required assessments between visits will be documented at the study required visits.

Subjects with a discharge date later than Week 8, who did not have an ileostomy, will have the last study visit on Week 8 ±14 days.

Diverted patients should receive routine endoscopic and/or contrast enema evaluation of the anastomotic region, between 3 weeks post-surgery and the Week 8 visit.

Subjects who present with a clinical suspicion of anastomotic leak during the study will have a CT scan with PO and, if necessary (e.g., presence of a diverting ileostomy), rectal contrast to confirm.

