### 10.2 Hypotheses

$$\begin{aligned} H_0: & \quad p_t = p_c \\ H_1: & \quad p_t < p_c \end{aligned}$$

Where  $p_t$  and  $p_c$  represent the expected population incidences of post-operative anastomotic leaks in the treatment (PERFUSION) and control groups, respectively. Within their respective treatment groups,  $p_t$  and  $p_c$  will be estimated as the number of subjects who experience a post-operative anastomotic leak according to the definition in Section 3.1, divided by the number of subjects who either are included in the numerator or are known to be free of such leaks as of the 8 weeks visit. Subjects without a known anastomotic leak but with less than 6 weeks of follow-up (i.e., insufficient follow-up to declare them "leak-free") will not be included in these estimates.

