4.4 Handling of missing and incomplete data

	Forms			
	Title	Statistical Analysis Plan Template		
	Code	Version	Effective Date	Page
	FRM_ST03_032	01	23 Apr 2015	15 of 20

The number of patients with missing data will be presented under the “Missing” category, if present. Missing values will be included in the denominator count when computing percentages.

When continuous data are being summarized, only the non-missing values will be evaluated for computing summary statistics.

A sensitivity analysis will also occur for the primary endpoint via a tipping point analysis. All missing data in the treatment group will be counted as failures while all missing data in the control group will be counted as successes. The p-values will be compared to the primary efficacy analysis to see if there is a difference in interpretation of results.

In general partial dates will be imputed as follows:

- if only the day is missing, the first day of the month will be assumed;
- if the day and the month are missing, January 1st will be assumed;
- if a date is completely missing or unknown the patient’s data will not be included for analysis

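### The synopsis ends ileostomy subjects' follow-up at closure if that precedes Week 8, against its own visit list, Protocol 3.1, 8.4 and 9.5, and SAP 3.2

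*Protocol*

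**What the plan says.** The Protocol Summary, under Study Procedures and Assessments, closes its follow-up bullet with: "The last study visit for subjects with an ileostomy will occur on the date of closure, or at Week 8, whichever is earlier". The same bullet opens with a list that contains both visits: "Follow-up visits on Day 1, date of discharge, Week 8, and date of ileostomy closure (if applicable"). The synopsis follow-up text says "All subjects will have study specific follow-up visits on Day 1, date of discharge, Week 8 and the date of ileostomy closure (if applicable"), and Protocol 3.1 repeats that sentence. Protocol 8.4 and SAP 3.2 both require "study specific visits on postoperative Day 1, the date of discharge, Week 8" (56 ±14 days), with the closure date in addition. Table 1 schedules a leak assessment at Week 8 with no exception for ileostomy subjects. Protocol 9.5 adds "All AEs will be followed throughout the study until the Week 8 visit".

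The primary estimate depends on length of follow-up. Under Protocol 10.2 and SAP 6.1, "Subjects without a known anastomotic leak but with less than 6 weeks of follow-up" are left out of the estimates, whereas any subject with a known leak is counted. In the SAP 4.4 sensitivity analysis, "All missing data in the treatment group will be counted as failures", and missing controls are counted as successes.

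On detection, Protocol 3.1 and Table 1 schedule endoscopy and/or contrast enema between Week 3 and Week 8 only for diverted subjects. In them a leak may be identified by sigmoidoscopy "or by rectal contrast imaging, regardless of presence or absence of clinical symptoms". Other subjects have a CT on clinical suspicion. Protocol 8.3.2.3 bases diversion on clinical judgment together with the perfusion assessment, and the Operative CRF (8.3) records whether an ileostomy was made.

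**The concern.** The synopsis sentence and the other passages cannot both be followed. Read literally, an ileostomy subject never has both visits unless they fall on the same day: an early closure removes the Week 8 visit, and a late closure removes the closure visit.

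The early case touches the primary endpoint. Leaks count up to Week 8, and a subject is leak-free only after sufficient follow-up. Ending follow-up at an early closure makes outcomes missing for an administrative reason, and the loss depends on outcome: leak-free subjects drop out of the denominator and subjects who leaked do not. A leak arising between an early closure and Week 8 may also go unrecorded.

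A separate and smaller point concerns reporting. Diverted subjects are screened for symptom-free leaks and others are not, and diversion is decided after randomization. A reader of the primary result would want diversion and route of detection by arm. The SAP names no such table.

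**Working it through.** **Inputs from the documents.** Leak rates 12.5% and 6.25%, planned N = 800 and interim N = 450, 1:1 (Protocol 10.4); pooled z-test without continuity correction, one-sided 0.025 (Protocol 10.3, SAP 6.1); 6-week exclusion (Protocol 10.2, SAP 6.1). SAP 3.3 fixes no sample size, so 400 and 225 per arm are illustrations.

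**Assumed, because the documents are silent.** Diversion d = 60% in both arms; a share c = 5-20% of diverted leak-free subjects closed before day 42.

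**The plan's own figure.** Pocock-type spending at t = 450/800 gives 0.0169 at the first look and critical values 2.122 and 2.220. Power at 12.5% v 6.25% with the pooled variance is 81.61%, against the stated 81.6%. This confirms the test set-up; the present point changes no stated figure.

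**Which closures matter.** Week 8 is day 56 ±14, so its window opens at day 42, which is also the 6-week limit. A closure from day 42 can fall inside the Week 8 window and leaves the subject evaluable. Only earlier closures remove a leak-free subject.

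**Effect on the primary estimate, 400 per arm.** Observed rate = leaks / (400 − leak-free × d × c). At 12.5% there are 50 leaks and 350 leak-free subjects; at 6.25%, 25 and 375.

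| c | 12.5% reads | 6.25% reads | Difference | Change from 6.25 pp | Ratio |
|---|---|---|---|---|---|
| 5% | 50/389.5 = 12.84% | 25/388.75 = 6.43% | 6.41 pp | +0.16 pp | 0.501 |
| 10% | 50/379 = 13.19% | 25/377.5 = 6.62% | 6.57 pp | +0.32 pp | 0.502 |
| 20% | 50/358 = 13.97% | 25/355 = 7.04% | 6.92 pp | +0.67 pp | 0.504 |

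If the true rate is 12.5% in both arms and diversion is equal, both arms read the same and the difference is 0. If diversion were 60% in one arm and 50% in the other, still with equal true rates, the gap would be 12.84 − 12.78 = 0.06 pp at c = 5% and 13.97 − 13.70 = 0.27 pp at c = 20%.

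**Effect on the worst-case analysis.** SAP 4.4 does not say whether subjects excluded for short follow-up count as missing there. If they do, k early-closed PERFUSION subjects give (25 + k)/400 against 50/400:

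- k = 8: 33 v 50, pooled rate 0.10375, SE 0.02156, z = 0.0425/0.02156 = 1.971, p = 0.0244, still significant.
- k = 9: 34 v 50, z = 1.845, p = 0.0325, significance lost. These are 9 of the 375 × 0.6 = 225 diverted leak-free PERFUSION subjects.

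At 225 per arm (14 v 28 leaks), k = 1 gives 15 v 28, p = 0.0186, and k = 2 gives 16 v 28, p = 0.0284. Two subjects, out of about 225 × 0.9375 × 0.6 = 127, are enough.

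**Scale of the detection point.** Let s be the share of leaks that are silent and found only by routine imaging, the same in all subjects, and let that imaging find them all. With equal true rates of 12.5%, the observed difference is 0.125 × s × (diversion gap between arms). The only documented change of diversion plan is 1 of 139 in PILLAR II (Protocol 1.2), a different population. Used as the gap, with s = 20-50%, it gives 0.02-0.04 pp and a one-sided false-positive rate of 2.4-2.6%. Assumed gaps of 10-20 points would give 0.8-6.6% in a single analysis at N = 450: above 2.5% if the PERFUSION arm diverts less, below it if it diverts more.

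**The case against.** The best defense is that the sentence stands alone against several passages, so sites would probably work from the body and Table 1. Leaks are reportable as SAEs (Protocol 9.4) and adverse events are followed to Week 8 (9.5), so many leaks after an early closure would still surface. This stands for recorded leaks. It does not establish that the remaining subjects are leak-free at 6 weeks, which the denominator requires.

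It is also fair that the worst-case fragility is not specific to this rule. SAP 4.4 turns any missing PERFUSION outcome into a leak, whatever the cause. The synopsis sentence would only be one avoidable source.

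On the reporting point, SAP 4.1 already says that categorical variables are summarized by group, which partly covers ileostomy as a CRF item, and Protocol 6.4 has concomitant diagnostic procedures such as endoscopy recorded with dates. What remains is that no by-arm table of diversion or detection route is named.

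A reader might infer that the sentence biases the comparison toward the device, or that routine imaging of diverted subjects inflates the type I error. The documents support neither. With equal true rates and equal diversion the first effect is zero. The second needs a diversion imbalance, and none is documented; its direction is open, and at the one documented frequency the error rate is essentially nominal.

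**Conclusion.** The contradiction is certain and rests on the text alone: the synopsis sentence is wrong as written against its own bullet, Protocol 3.1, 8.4 and 9.5, and SAP 3.2. Its effect on the primary endpoint is conditional on a site following it and on closures before day 42, and its size cannot be derived from the documents. Under the assumed inputs it raises the level of the leak rates (12.5% reads up to 13.97%) far more than it alters the comparison: no shift with equal true rates and equal diversion, at most 0.67 pp at the design rates with equal diversion, and a nearly constant rate ratio. The worst-case analysis is more exposed, losing significance with 9 subjects at 400 per arm or 2 at 225 per arm, but only if early-closed subjects count as missing there. It would be too strong to infer that every early closure costs an evaluable subject, since those from day 42 need not. The diversion table is an optional reporting improvement. Overall this is a minor correction.

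**What to change.** Reconcile the last sentence of the synopsis follow-up bullet with the rest of the synopsis, Protocol 3.1, 8.4 and 9.5, and SAP 3.2, so that primary-endpoint leak status is collected to Week 8 for every subject and the closure visit is additional. This concerns data collection only; it proposes nothing about who is diverted or imaged, or when an ileostomy is closed. State in SAP 4.4 whether subjects excluded for under 6 weeks of follow-up count as missing in the worst-case analysis.

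Optionally, name in SAP 6.1 a by-arm summary of diversion, and of leaks found at routine Week 3-8 imaging versus on clinical suspicion.

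The cost is one synopsis sentence, one clarifying SAP sentence, a Week 8 contact for subjects closed early and, if adopted, one table. SAP 1.0 is dated 10 April 2017. Counting back 70 days, subjects operated on before 30 January 2017 were by then past their Week 8 window. For them, any missing leak status must be abstracted from existing records, such as adverse event onset dates and dated imaging procedures. Some detection routes may not be recoverable.
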